27.1 Analysis of the primary outcome

The primary objective of the NIS trial is to estimate and test treatment differences in leg pain intensity at 10 days after commencement of Naproxen or placebo. Multiple measurements taken on the same patient will be correlated. This is accounted for in the analysis by a mixed effects model; either a linear mixed model (LMM) or a generalized linear mixed model (GLMM) depending on the distribution of the leg pain intensity. The model includes fixed effects for treatment, time (11 time points), the treatment-by-time interaction, and baseline measurements of leg pain plus age and gender. The primary result will be the treatment effect estimates over the period of treatment with 95% CI.

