# **9 STATISTICAL METHODS AND DATA ANALYSIS**

## **9.1 DETERMINATION OF SAMPLE SIZE**

The sample size calculation is based on a mean difference between the Naproxen group and the placebo group of 1.5 (0-10) at ten days with a SD of 2.5 using a two-sample t test. There is no robust evidence for the smallest worthwhile

between group pain relieving effect in sciatica. In previous sciatica studies sample size were calculated based on between group differences of 1.5 and 1.0 [80, 81]. In a recent RCT of pregabalin the sample size was calculated based on a between group difference of 1.5 [36]. In knee osteoarthritis, a condition in which NSAIDs are generally recommended, the treatment effect of NSAIDs is about 1.0 [82-84]. The estimated SD of 2,5 is based on a recent Cochrane review of NSAID studies in sciatica [30].

Assuming 90% power and a two-tailed 5% significance level a sample size of 60 subjects is needed in each treatment arm. Allowing for a combined dropout and non-compliance rate  $\leq 20\%$  [85] the total number of subjects will be 150.

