8.2 Secondary objectives

To demonstrate that, in patients with sciatica, treatment with Naproxen 500 mg twice daily is superior to placebo with respect to

- improvement in back pain intensity
- improvement in disability
- use of rescue medication
- global perceived change in sciatica/back problem
- improvement in sciatica symptom bothersomeness
- 30% and 50% improvement in leg pain
- concomitant use of opioid analgesics
- ability to work and study

STUDY METHODS

9 Trial Design

NIS is a multicenter, two-armed randomized, placebo controlled, double blind, parallel group, superiority phase IV trial.

10 Randomization

Study medicines will be packaged and labelled according to a pre-generated random number sequence; each sealed box will have a unique participant number. Computer-generated block randomization, stratified by center, will be used. Allocation to Naproxen or placebo will be at a 1:1 ratio.

11 Sample size

The sample size estimation is based on a minimum difference of interest between the Naproxen group and the placebo group of 1.5 at day 10. Assuming a standard deviation SD of 2.5 (see protocol for details and references), 90% power and a two-tailed 5% significance level, 60 subjects in each treatment arm is required. Allowing for a combined dropout and non-compliance rate $\leq 20\%$ a sample size of 150 was determined.

12 Framework

Analyses will be within a superiority hypothesis testing framework, comparing Naproxen to placebo.

13 Interim analyses and stopping guidance

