27.2 Analysis of secondary outcomes

- Back pain intensity will be analyzed using the same model used to analyze the primary outcome.
- Disability and sciatica bothersomeness will be analyzed using the same model used to analyze the primary outcome, but with 3 time points.
- Responder analyses, i.e. 30% and 50% improvement in leg pain intensity, will be performed using a mixed effects logistic regression model to obtain estimates of odds ratios (OR) and 95% CI. Based on the absolute risk reduction (ARR) between Naproxen and placebo we will calculate the numbers needed to treat (NNT) with 95% CI (NNT = 1/ARR).
- Rescue medication consumption and concomitant use of opioids during the treatment period will be analyzed using a suitable regression.
- Work/Study is an unordered categorical variable. The appropriate model is therefore a multinomial with repeated measurements and it will be analyzed using a GLMM.
- Global perceived change is an ordered categorical variable with repeated measurements and will be analyzed using a GLMM.

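### SAP 27.1 gives baseline leg pain one slope for all days; if the slope differs between days, the day-10 contrast loses a little precision, and a baseline-by-time term removes the loss at almost no cost

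*SAP*

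**What the plan says.** SAP 27.1 defines the primary mixed model: "The model includes fixed effects for treatment, time (11 time points), the treatment-by-time interaction, and baseline measurements of leg pain plus age and gender". Baseline appears as a main effect. Neither SAP 27.2 to 27.5 nor Protocol 9.5.1 adds a baseline-by-time term, and SAP 27.3 says only that analyses are adjusted for the baseline value of the outcome where one exists.

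SAP 27.2 carries the model over: "Back pain intensity will be analyzed using the same model used to analyze the primary outcome". RMDQ-S and SBI use it too, with three time points.

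SAP 15 has leg pain recorded daily from day 0 to day 10, which makes 11 occasions, and RMDQ-S and SBI recorded on days 0, 5 and 10. The counts in 27.1 and 27.2 therefore suggest that day 0 is both a response and the covariate. Protocol 6.5.1 defines baseline pain as the mean of two day-0 ratings.

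Two statements in SAP 27.1 bear on which contrast matters. The objective is to "estimate and test treatment differences in leg pain intensity at 10 days after commencement of Naproxen or placebo", but the section ends: "The primary result will be the treatment effect estimates over the period of treatment with 95% CI". The sample size (Protocol 9.1, SAP 11) rests on day 10.

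On the random part, Protocol 9.5.1 names a random intercept. SAP 27.1 names no covariance structure.

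**The concern.** A common slope is the most efficient adjustment for day 10 only if it equals the day-10 slope. There are two reasons to doubt that it does.

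- **Day 0 as a response.** The slope of a day-0 response on baseline is 1 by construction for RMDQ-S and SBI, and at or near 1 for leg pain. A day-10 slope of 1 as well would be a coincidence.
- **Change over ten days.** Protocol 1.4.5 expects all patients to improve over time. A weaker link between baseline and day-10 pain is plausible, although the documents give no data on it.

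If the slopes differ, the fitted common slope is a compromise between days. The day-10 difference, on which the trial is sized, then gains less from baseline adjustment than the same data could give. What is at stake is part of the precision gained by adjusting.

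**Working it through.** **The plan's own figure.** Protocol 9.1 uses a "mean difference between the Naproxen group and the placebo group of 1.5 (0-10) at ten days with a SD of 2.5" in a two-sample t test and states: "Assuming 90% power and a two-tailed 5% significance level a sample size of 60 subjects is needed in each treatment arm".

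- Normal formula: n = 2 × (1.960 + 1.282)² × 2.5² / 1.5² = 58.4, so 59 per arm. The exact t test gives 59.35, so 60.
- 60 / 0.8 = 75 per arm, 150 in total. The stated size is reproduced.
- Power at 60 per arm, normal formula: Φ(1.5 / √(2 × 6.25 / 60) − 1.960) = Φ(1.326) = 0.908, with no baseline adjustment.

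**Formulas.** With complete data and a free treatment-by-time mean structure, a common slope b gives a day-10 contrast equal to the day-10 difference minus b times the baseline difference. Write SD0 for the baseline SD, r10 for the day-10 correlation with baseline, and β10 = r10 × 2.5 / SD0 for the true day-10 slope.

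- Residual variance with a day-specific slope: V = 2.5² × (1 − r10²).
- Variance ratio, common against day-specific slope: 1 + (b − β10)² × SD0² / V.
- Power: Φ(1.5 / √(2 × V × ratio / 60) − 1.960).

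**Assumptions not in the documents.** SD0 is 1.5 or 1.8. The correlation falls in a straight line from 0.85 on day 1 to r10 on day 10. The SD rises in a straight line from SD0 on day 0 to 2.5 on day 10. The slope on day t is r_t × SD_t / SD0.

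**Which b results.** Under a random intercept, days are weighted equally and b is the mean of the daily slopes. If day 0 is a response, a slope of 1 is added to that mean. Under an unstructured covariance, b is the generalised least squares slope over days 1 to 10, computed with AR(1) residual correlation from 0.8 to 0.95.

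**Central case, SD0 = 1.8 and r10 = 0.4.**

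- β10 = 0.4 × 2.5 / 1.8 = 0.556; V = 6.25 × 0.84 = 5.25.
- The ten daily slopes run from 0.883 to 0.556 and sum to 7.43. Days 1–10: b = 0.743. Days 0–10: b = (7.43 + 1) / 11 = 0.766.
- Ratio, days 0–10: 1 + (0.766 − 0.556)² × 3.24 / 5.25 = 1.027. Power is 0.943, against 0.948 with a day-specific slope.

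**All cases.**

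| SD0 | r10 | β10 | Ratio, random intercept, days 1–10 | Ratio, random intercept, days 0–10 | Ratio, unstructured | Power: day-specific / random intercept 0–10 / worst unstructured |
|---|---|---|---|---|---|---|
| 1.5 | 0.5 | 0.833 | 1.002 | 1.003 | 1.002 | 0.967 / 0.966 / 0.966 |
| 1.5 | 0.4 | 0.667 | 1.011 | 1.013 | 1.021–1.028 | 0.948 / 0.945 / 0.942 |
| 1.5 | 0.3 | 0.500 | 1.025 | 1.030 | 1.055–1.079 | 0.931 / 0.924 / 0.912 |
| 1.8 | 0.5 | 0.694 | 1.009 | 1.012 | 1.018–1.030 | 0.967 / 0.965 / 0.962 |
| 1.8 | 0.4 | 0.556 | 1.022 | 1.027 | 1.050–1.084 | 0.948 / 0.943 / 0.931 |
| 1.8 | 0.3 | 0.417 | 1.039 | 1.048 | 1.096–1.160 | 0.931 / 0.920 / 0.892 |

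**Bias.** In a simulation of 4,000 trials with 60 per arm, the adjusted day-10 estimates averaged −1.49 to −1.50 for a true −1.5. For correlations falling from 0.7 to 0.3 (SD0 1.5), 0.8 to 0.2 (SD0 1.5) and 0.8 to 0.2 (SD0 2.0), the variance ratios were 1.005, 1.034 and 1.078 with a random intercept on days 0–10, and 1.009, 1.074 and 1.16 with an unstructured covariance on days 1–10.

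**The case against.** The other side has five good points.

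- **The weakening link is not documented.** Neither document gives a baseline SD, a correlation or a daily course. The slope is the correlation times the ratio of SDs, so a rising SD can offset a falling correlation. With SD0 = 1.5 and r10 = 0.5 the loss is 0.2 to 0.3%. This stands: decay after day 0 is an assumption.
- **The larger losses need a covariance that the documents do not name.** Under the protocol's random intercept, the early days get no extra weight. This stands, although the SAP does not commit to the random intercept either.
- **The primary result may be an average over days.** The last sentence of SAP 27.1 permits that reading. Under a random intercept, the mean slope is then the right one and the loss essentially disappears. This stands, but the objective and the sample size point to day 10.
- **The sizing did not count on adjustment.** It uses SD 2.5 unadjusted, so even an imperfect adjustment usually leaves power above plan. This stands for every random-intercept case in the table.
- **SAP 27.4 lets the model change if assumptions fail.** This helps little: it does not name this term, and it leaves the choice until the data are seen.

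A reader might infer that the common slope biases the effect by over-correcting chance baseline imbalance. The documents do not support that. Imbalance averages zero under randomisation, and its contribution is already the (b − β10)² × SD0² term, so counting it as a separate harm would count the same loss twice. Dropout related to baseline could add some bias; that was not computed.

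A reader might also infer that the planned power is lost. Within the assumed ranges, that happens only with steep decay combined with an unstructured covariance.

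**Conclusion.** The gap in the text is certain: the listed model forces one baseline slope on all days while letting treatment vary by day. The consequence is a modest loss of precision at day 10.

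On the stated assumptions, day-10 variance rises by about 0.2 to 5% under a random intercept. That costs at most about 1 point of power (0.931 to 0.920), so the planned 90% is kept. Under an unstructured covariance the rise is about 0.2 to 16%. In the worst case, power falls from 0.931 to 0.892, below the 0.908 of an unadjusted comparison.

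These figures assume complete data on 60 per arm and use the true variance of the contrast rather than the model's own standard error. They were computed for leg pain only. For RMDQ-S and SBI, the argument rests on day 0 being a response, and no size was derived.

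This is a minor efficiency improvement that does not affect the validity of the trial.

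**What to change.** In SAP 27.1, and for back pain, RMDQ-S and SBI in SAP 27.2:

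- Add a baseline-by-time interaction with time as a categorical factor.
- Use only post-baseline days as responses: days 1 to 10 for leg and back pain, days 5 and 10 for RMDQ-S and SBI. Correct the counts of time points to match.
- Take the day-10 contrast stated in the objective from that model, and reconcile the closing sentence of 27.1 with it.
- Name the covariance structure, since the size of the loss depends on it.

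The cost is about 9 degrees of freedom for each diary outcome (10 days minus 1) and 1 each for RMDQ-S and SBI (2 days minus 1). It needs no new data and no extra patients. The change should be fixed before unblinding, and preferably before any results by coded arm are seen.

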### 2.4 SECONDARY ENDPOINTS

- The change in back pain (24 hours average) rated on a 0-10 numeric rating scale (NRS) from baseline to day 10 based on longitudinal analyses of daily observations.
- The change in disability assessed by the Roland Morris Disability Questionnaire for sciatica (RMDQ-S) based on longitudinal analyses of observations at baseline, day 5 and day 10.
- The use of rescue medication, i.e. number of Paracetamol tablets taken between baseline and day 10.
- The number of patients who at day 5 and day 10 report their pain to be *completely gone, much better and better* on a Global Perceived Change (GPC) scale
- The change in sciatica symptoms assessed by the Sciatica Bothersomeness Index (SBI) based on longitudinal analyses of observations at baseline, day 5 and day 10.
- The number of patients who at day 5 and day 10 have a (i)  $\geq 30\%$  and a (ii)  $\geq 50\%$  reduction in leg pain score relative to baseline
- The use of (i) weak opioids and (ii) strong opioids assessed by the number of Defined Daily Doses (DDD) between baseline and day 10
- The number of patients who at day 10 are able to work/study as normal

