13.2 Early stopping

The safety profile of Naproxen is well documented and established, and the dosing is under its approved label use. There is no reason to expect Naproxen to affect the rate of serious sciatica complications such as lower extremity paresis or cauda equina syndrome. As Naproxen is used under its approved label use no interim safety analyses will be conducted.

14 Timing of final analysis

All outcomes will be analyzed jointly after the end of the trial, i.e. after the last visit of the last subject, and data locking.

15 Timing of outcome assessments

Primary outcome: Leg pain (the primary outcome) is measured daily from baseline (day 0) to end of treatment (day 10).

Secondary outcomes

- Back pain is measured like leg pain
- Disability, assessed by the Roland Morris Disability Questionnaire for Sciatica (RMDQ-S), is measured at day 0, 5 and 10
- Rescue medication consumption is measured (i) at the end-of study-visit (by pill count) and (ii) daily from day 1 to day 10 (by self-report).
- Global perceived change is measured at day 5 and 10.
- Sciatica bothersomeness, assessed by the Sciatica Bothersomeness Index (SBI), is measured at day 0, 5 and 10.
- Concomitant use of opioid analgesics is assessed on day 0, 5 and 12 (± 2).
- The ability to work or study is measured at day 0 and 10.

Table 1. Timing of outcome assessments

	Baseline	Start of treatment				End of treatment	End of study
–							

Day	0	1	2-4	5 (± 1)	6-9	10	12 (± 2)
	Visit	Home	Home	Home	Home	Home	Visit
-Leg pain -Back pain	X	X	X	X	X	X	X
-SBI -RMDQ-S	X			X		X	X
Global perceived change				X		X	X
Work/study	X					X	X
Rescue medication (pill count)							X
Rescue medication (self-report)		X	X	X	X	X	
Opiod use	X			X			X

SBI Sciatica Bothersomeness Index, RMDQ-S Roland Morris Disability Questionnaire for Sciatica.

Visit windows.

Patient reported outcomes are captured using a web based real-time electronic diary (ViedocMe). The questionnaires are available 24 hours on the scheduled date. The end of study visit is scheduled on day 12 (± 2).

STATISTICAL PRINCIPLES

16 Level of statistical significance

A two-tailed p value of less than 0.05 is considered to indicate statistical significance. We will report nominal p values.

17 Adjustment for multiplicity

We will not adjust for multiple comparisons. This trial has one primary outcome which will be analyzed in a single mixed-effect model and there are no planned subgroup analyses.

18 Confidence intervals

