27.3 Adjustment for covariates

The statistical analyses of primary and secondary efficacy outcomes will be adjusted for baseline measures of the outcome where one is available [5]. The analysis of rescue medication consumption and use of concomitant opioids will be adjusted for baseline leg or back pain intensity depending on which is worse.

Study center (stratification variable) will not be included as covariate as we expect the majority of participants to be included at one center (Østfold). We will perform a sensitivity analysis with and without adjusting for center. Provided that a sufficient number of patients are included from at least 4 centers, these can be treated as additional random effects in the model.

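### SAP 27.1–27.2 do not name the outcome days; the likeliest reading makes day 0 both outcome and covariate, so standard errors of level contrasts are too small, chiefly for RMDQ-S and SBI

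*SAP*

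**What the plan says.** SAP 27.1 lists fixed effects for treatment, "time (11 time points), the treatment-by-time interaction, and baseline measurements of leg pain", plus age and gender. SAP 27.2 says that RMDQ-S and SBI "will be analyzed using the same model used to analyze the primary outcome, but with 3 time points", and applies the leg pain model unchanged to back pain. SAP 27.3 repeats that efficacy analyses "will be adjusted for baseline measures of the outcome where one is available". None of these sections lists the days that enter the model as outcomes.

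The days appear in SAP 15. For pain: "Leg pain (the primary outcome) is measured daily from baseline (day 0) to end of treatment (day 10". For disability: "Disability, assessed by the Roland Morris Disability Questionnaire for Sciatica (RMDQ-S), is measured at day 0, 5 and 10", and SBI follows the same days. Protocol 2.4 describes the RMDQ-S and SBI endpoints as "based on longitudinal analyses of observations at baseline, day 5 and day 10". SAP Table 1 also marks pain, SBI and RMDQ-S at the end-of-study visit on day 12 (± 2), after treatment has ended.

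On the target, SAP 27.1 opens with the difference at 10 days and closes with: "The primary result will be the treatment effect estimates over the period of treatment with 95% CI". Protocol 2.3 and 9.5.1 and planned Table 2 speak of change from baseline, and Table 2 reports least-squares means. The SAP's analysis section names no covariance structure; protocol 9.5.1 names a random intercept. Protocol 6.5.1 defines baseline pain as the mean of two day-0 recordings, one at the clinic and one at home that evening.

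**The concern.** If day 0 is a response row and baseline is also a covariate, the model regresses the day-0 value on itself. For RMDQ-S and SBI the two are the same number. That row has almost no residual variation. A random-intercept model with one common baseline slope and one common residual variance therefore pulls the slope up and the estimated variance down for the days that matter. The estimated treatment effect stays unbiased, but the interval around a difference in level is too narrow.

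Day 0 is one row in three for RMDQ-S and SBI and one in eleven for pain, so the secondary scales are hit hardest. The SAP seeks to show superiority on them and reports nominal p values without multiplicity adjustment (SAP 8.2, 16, 17). For pain there is a further gap: no section says whether the day-0 response would be the clinic score, the evening score or their mean.

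**Working it through.** **Counts.** Days 0 to 10 give 11 rows and days 0, 5 and 10 give 3, which are the SAP's counts. Post-baseline days alone give 10 and 2. The rival reading from SAP Table 1 drops day 0 and adds day 12: days 1–10 and 12 (11 rows), or days 5, 10 and 12 (3 rows). It avoids the double use but brings in an off-treatment value, and the text of SAP 15 stops at day 10.

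**Model examined.** Day-0 rows included, baseline covariate (SAP 27.1, 27.3), random intercept (protocol 9.5.1). Assumed, not in the documents: constant correlation r of 0.3–0.7, equal variances (set to 1), no treatment effect, complete Gaussian data.

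**Formulas.** J is the number of rows and k = J − 1 the number of post-baseline rows. The common factor 2/n cancels.

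- Common slope: b = [1 + (J − 1)r]/J
- Residual variance of the patient mean: b − b²; within-patient variance: w = 1 − r
- Day 10: model variance b − b² + w(1 − 1/J); true variance 1 − 2br + b²
- Post-baseline average: model variance b − b² + w(1/k − 1/J); true variance [1 + (k − 1)r]/k − 2br + b²
- SE ratio = √(model/true); type I error = 2[1 − Φ(1.96 × ratio)]

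**Three rows, r = 0.5.** b = 2/3.

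- Day 10: model 0.222 + 0.5 × 0.667 = 0.556; true 1 − 0.667 + 0.444 = 0.778; ratio 0.845. The model value is the average of the three residual variances, (0.111 + 0.778 + 0.778)/3, so the near-empty day-0 row does the damage.
- Average of days 5 and 10: model 0.222 + 0.5 × (0.5 − 0.333) = 0.306; true 0.75 − 0.667 + 0.444 = 0.528; ratio 0.761.

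**Eleven rows, r = 0.5, single day-0 value.** b = 6/11 = 0.545.

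- Day 10: 0.248 + 0.5 × 10/11 = 0.702 against 0.752; ratio 0.966.
- Average of days 1–10: 0.248 + 0.5 × (0.1 − 0.0909) = 0.2525 against 0.3021; ratio 0.914.

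| Outcome, contrast | SE ratio, r = 0.3 / 0.5 / 0.7 | Type I error |
|---|---|---|
| RMDQ-S, SBI: day 10 | 0.861 / 0.845 / 0.832 | 9.1–10.3% |
| RMDQ-S, SBI: average of days 5 and 10 | 0.771 / 0.761 / 0.753 | 13.1–14.0% |
| Pain: day 10 | 0.974 / 0.966 / 0.960 | 5.6–6.0% |
| Pain: average of days 1–10 | 0.915 / 0.914 / 0.914 | 7.3% |

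**Pain with two day-0 recordings.** The covariate is their mean, and their mutual correlation is assumed to be r, 0.8 or 0.9. The day-10 ratio is 0.956–0.972 if the mean is also the response and 0.964–0.981 if the evening score is. The day 1–10 average gives 0.915–0.928. Across both versions the SE is 1.9–4.4% too small at day 10 (type I error 5.4–6.1%) and 7.2–8.5% too small for the average (6.9–7.3%).

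**Day 0 removed.** The slope becomes r, and model and true variance at day 10 are both 1 − r². The ratio is 1.000 at day 10 and for the average.

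**Change contrast.** For day 10 minus day 0 by arm, with equal variances, the covariate cancels and both variances are 2(1 − r), so the ratio is 1.000. Against the covariate-adjusted 1 − r², the variance is larger by the factor 2/(1 + r): 1.18 at r = 0.7 and 1.54 at r = 0.3.

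**Simulation.** With 75 per arm, age and gender in the model and 6,000 replicates per scenario, three rows gave type I error of 9.1–10.4% (day 10) and 12.5–14.3% (average); eleven rows gave 5.6–6.3% and 6.7–7.8%. With about 20% missing-at-random dropout, three rows gave 10.1–11.7% and 14.3–15.6%, and eleven rows 5.6–6.8% and 7.4–8.1%. With day 0 removed, all were 4.7–5.6%.

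**Decaying correlation, a separate matter.** At an assumed 0.90 or 0.93 per day, with SD constant or rising from 1.75 to 2.5, the pain day-10 type I error is 11.7–17.0% with day 0 and still 10.1–15.0% without it. Post-baseline averages return to a ratio of 1.000 once day 0 is removed.

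**The case against.** The strongest objection concerns the contrast. The protocol endpoint, protocol 9.5.1 and planned Table 2 all speak of change. If day 0 is a row, the obvious change estimate is the treatment-by-time contrast of day 10 against day 0, and its SE is right under constant correlation and equal variances. This stands, and it limits the point to level contrasts. It does not remove the point. SAP 27.1 also speaks of the difference at 10 days, and Table 2 uses least-squares means. A least-squares-mean difference at day 10 is affected even when change is the response, because that is the same model with the slope shifted by 1. The change contrast also pays 18–54% in variance.

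Second, the quantified model is assembled from two documents: the covariate from the SAP, the random intercept from the protocol and an inferred day-0 row. With change as the response, the RMDQ-S and SBI day-0 rows would be zero for everyone, and an analyst might well drop them. This stands too: the error rates are conditional, and no other covariance model was fitted. The latitude in SAP 27.4 to change models answers assumptions that the data challenge; it does not define the outcome rows.

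A reader might infer that the primary day-10 test is seriously inflated, or that every interval in the plan is too narrow. The documents support neither: the pain day-10 effect is small under constant correlation, and the change contrast is unaffected. Nor should the 11.7–17.0% under decaying correlation be laid to the baseline; most of it comes from the random intercept.

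**Conclusion.** The SAP should be corrected on this point. What the text establishes is that the outcome days, the contrast and the covariance structure are not stated, and that the counts fit the SAP 15 text only with day 0 as an outcome beside a baseline covariate.

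On that reading, level contrasts for RMDQ-S and SBI are materially anti-conservative. Those for pain are slightly so at day 10 and moderately so for a treatment-period average. Medication starts the morning after day 0 (protocol 6.2.2), so an average over the treatment period most naturally means post-baseline days. The sizes rest on the day-0 reading, a random intercept and an assumed constant correlation of 0.3–0.7. On the day-12 reading there is no double use. The point estimates and the sample size are not affected. Confidence is medium, because the model has to be inferred.

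**What to change.** In SAP 27.1 and 27.2, choose one of two forms:

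- List post-baseline outcome days only (days 1–10 for leg and back pain; days 5 and 10 for RMDQ-S and SBI) and keep baseline as a covariate, preferably with a baseline-by-time term.
- Keep day 0 as an outcome, drop the baseline covariate, constrain the arms to be equal at day 0, and say which day-0 pain value is the response.

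State the day-10 difference as the primary contrast, and name the days of any average reported.

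Separately, name a covariance structure that allows variance and correlation to differ over days, with a fallback. An unstructured matrix for 10 days has 10 × 11/2 = 55 parameters. Removing day 0 does not cure a random intercept that understates the day-10 SE when correlation decays.

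The cost is wording and code; no data or patients are added. The covariate form drops randomized patients with no post-baseline value from the likelihood; the constrained form keeps them.
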